# 8. STATISTICAL DESIGN AND METHODS

Statistical analysis of primary study outcome will be based on calculation of 95% confidence interval (CI) of the estimated accuracy of Vitastiq readings for each mineral or vitamin. The expected accuracy level is 70%, therefore by using 135 readings the radius of 95% confidence interval would be estimated with 10% relative margin of error. The point estimate of the accuracy value together with 95% CI will be presented for each mineral or vitamin.

Statistical analysis of secondary outcomes will include Kappa statistic for interrater reliability on Vitastiq readings or Friedman ANOVA for testing the possible change of each mineral/vitamin blood level during the study period. Kappa statistic for interrater reliability will be calculated separately for each analyte (vitamin and mineral) and for all 135 readings. Additionally, the results of the second and the third rater (second investigator and participant) will be separately compared to the results of the first rater (first investigator). In Friedman ANOVA test 3 consecutive blood test results, that is on day  $1, 29 \pm 4$  days and  $57 \pm 4$  days, will be compared.

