#### 2.2 STUDY ENDPOINTS

## 2.2.1 Primary endpoint

The primary endpoint of the study is to determine the Vitastiq device accuracy and performance. The goal is to achieve at least 70% Vitastiq accuracy performance meaning that at least 70% of Vitastiq readings for each mineral and vitamin fall within the range of matching blood test results. Vitastiq readings will be presented as low, normal and high, where:

- low means below the agreed normal level for selected mineral or vitamin determined by biochemical blood analyses tests (see Table 1)
- normal means within the range of agreed normal level and
- high means above the agreed normal level.

Data will be collected from Vitastiq device utilizing 45 volunteers. Volunteers will visit the site three times (day 1,  $29 \pm 4$  days and  $57 \pm 4$  days). Three complete Vitastiq readings by two investigators (who differs in years of experiences in performing EAV by Vitastiq device) and by the participant in the study will be performed at each visit (altogether, 405 Vitastiq readings will be collected on visit days (day 1,  $29 \pm 4$  days and  $57 \pm 4$  days) for 45 volunteers). To confirm the primary endpoint only Vitastiq readings performed by the most experienced investigator in acupuncture will be taken to evaluate the accuracy. Therefore, 135 Vitastiq readings taken on visit days (day 1,  $29 \pm 4$  days and  $57 \pm 4$  days) will be compared to blood test results. Analyses of Vitastiq data generated by matching minerals and vitamins levels to venous blood minerals and vitamins concentration by well-established analytical methods on day 1,  $29 \pm 4$  days and  $57 \pm 4$  days will determine Vitastiq device accuracy and performance.

Table 1: Agreed normal levels of vitamins and minerals in blood serum (fasting).

Mineral/Vitamin	Low	Normal	High	
Sodium	< 135 mmol/L	135 – 145 mmol/L	> 147 mmol/L	
Potassium	< 3.8 mmol/L	3.8 – 5.5 mmol/L	> 5.5 mmol/L	
Calcium	< 2.15 mmol/L	2.15 – 2.55 mmol/L	> 2,55 mmol/L	
Magnesium	0,66 mmol/L	0,66 – 1,07 mmol/L	> 1,07 mmol/L	
	Men: < 10,6 μmol/L	Men: 10,6 – 28,3 μmol/L	Men: > 28,3 μmol/L	
Iron	Women: < 6,6 μmol/L	Women: 6,6 – 26,0 μmol/L	Women: > 26,0 μmol/L	
Zink	< 70 μg/dL	70 – 150 μg/dL	> 150 μg/dL	
Selenium	< 50 μg/L	50 – 120 μg/L	> 120 μg/L	
Folic acid	< 7,0 nmol/L	7,0 – 46,4 nmol/L	> 46,4 nmol/L	
Vitamin A	< 250 μg/L	250 – 1100 μg/L	> 1100 μg/L	
Vitamin B12	< 138 pmol/L	138 – 652 pmol/L	> 652 pmol/L	
Vitamin D	< 30 μg/L	>30 µg/L	/	

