#### 3.2 RECRUITMENT AND RETENTION

Volunteers will be screened for the inclusion and exclusion criteria and up to 50 volunteers will be enrolled. At least 45 volunteers should complete the study. Volunteers will be invited to join the study by public announcement on the web page of the Vizera, d.o.o., Ljubljana, Slovenia (www.vizera.eu). The invitation will be also shared on social media (facebook, linkedin, twiter). Viewers of the

advertisement will be invited to inform their colleagues and friends about the possibility to collaborate in the study.

Considering that participants will need to perform EAV using Vitastiq device every day of the study and visit a site for 4 times (screening visit + 3 visits), their participation will be compensated with 40 € (bruto) and a Vitastiq device will be given to them for their permanent use. Additionally, participant will receive the results of screening medical examination and blood tests results of all visits.

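### At the assumed 70% accuracy, 135 readings give a relative margin of 11.0% even if independent, not the stated 10%, which needs about 165 independent readings

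*Combined protocol and SAP*

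**What the plan says.** The primary analysis in Section 8 rests on "calculation of 95% confidence interval (CI) of the estimated accuracy of Vitastiq readings for each mineral or vitamin". The same section takes 70% as the expected accuracy and states that "by using 135 readings the radius of 95% confidence interval would be estimated with 10% relative margin of error". The Protocol Summary, under statistical analysis, carries the same sentence.

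Section 2.2.1 shows where the 135 comes from: "Data will be collected from Vitastiq device utilizing 45 volunteers. Volunteers will visit the site three times". Only the most experienced investigator's readings count for the primary endpoint, so each person contributes one reading per analyte per visit, and 45 × 3 = 135. Section 3.2 adds that "up to 50 volunteers will be enrolled. At least 45 volunteers should complete the study", so 135 is the count if exactly 45 people complete all visits.

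The text gives no formula for the margin, names no interval method, and does not mention that readings are repeated within a person.

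**The concern.** The sentence supplies every input needed to check it (accuracy, number of readings, confidence level and margin), and the inputs do not agree with one another. At 70% accuracy, 135 readings give a wider interval than stated.

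This is the only precision justification for the 135 readings in the text. The interval for each analyte is the primary result, and the accuracy goal is the same 70% that is assumed for planning. Readers will therefore look at how tightly each interval sits around 70%, and the plan leads them to expect narrower intervals than the design gives. The independence behind any such calculation is also unstated, although the design has three readings per person.

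**Working it through.** **Inputs.** Accuracy p = 0.70, two-sided 95% interval (z = 1.96), n = 135 and relative margin r = 0.10, all from Section 8. There are 45 participants with 3 visits each (Section 2.2.1). The relative margin is taken as half-width divided by the estimate.

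**1. The plan's figure.** 0.10 × 0.70 = 0.070, so the stated margin is a half-width of 7.0 points (63.0% to 77.0%).

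**2. The half-width with 135 independent readings.** z√(p(1−p)/n) = 1.96 × √(0.21/135) = 0.0773, or 7.7 points (62.3% to 77.7%). Relative: 0.0773/0.70 = 11.0%. The stated 10% is not reproduced.

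**3. Readings needed for 10% relative.** n = z²(1−p)/(p r²) = 1.96² × 0.30/(0.70 × 0.01) = 164.6, so 165. Relative to that, 135 is (165 − 135)/165 = 18% short.

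**4. Other two-sided interval methods.** At 94 or 95 correct out of 135:

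| Method | Half-width / estimate |
|---|---|
| Wilson, Agresti-Coull, Jeffreys | 10.8% to 11.1% |
| Exact (Clopper-Pearson) | 11.4% to 11.6% |

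The number of readings needed for a 7-point half-width is 162 (Wilson), 163 (Jeffreys, Agresti-Coull) or 177 (exact).

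**5. Other readings of the sentence.**
- Absolute margin of 10 points: n = 1.96² × 0.21/0.01 = 80.7, so 81.
- One-sided 95% bound (z = 1.645): 9.3% relative at n = 135; 10% would need 116.
- All 50 permitted enrolees completing, 150 readings: 7.3 points, 10.5% relative.
- Accuracy at which 135 independent readings do give 10%: p = 1/(1 + 0.01 × 135/1.96²) = 0.74.

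None of these yields 135 at 70% accuracy with a two-sided 95% interval and a 10% relative margin.

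**6. Repeated readings.** With three readings per person the variance is multiplied by 1 + 2 × ICC, where ICC is the within-person correlation of being correct for a given analyte. The documents give no ICC, so the values below are assumptions.

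| Assumed ICC | Half-width at 70% | Relative margin |
|---|---|---|
| 0 | 7.7 points | 11.0% |
| 0.2 | 9.1 points | 13.1% |
| 0.5 | 10.9 points | 15.6% |
| 0.8 | 12.5 points | 17.8% |
| 1 (upper limit) | 13.4 points | 19.1% |

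A 10% margin at 70% accuracy would require 1 + 2 × ICC = 135/164.6 = 0.82, that is, an ICC of about −0.09.

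**The case against.** The strongest reply is that the error is small and has no consequence for any decision. Under independence the gap is 0.7 points. The goal is a proportion of at least 70%, which does not depend on the interval, and the actual intervals will be reported for every analyte. This stands, and it limits the weight of the point.

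It can also be said that 135 was never derived from a 10% target: it is 45 people times three visits, and the sentence merely describes the resulting precision. That is a fair reading. The 165 should then be taken as a measure of the discrepancy and not as a failed sample-size calculation. The description is still wrong.

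Two reinterpretations would make 135 readings sufficient under independence: an absolute 10-point margin, or a one-sided 95% bound, which suits a goal of the at-least kind. The text, however, specifies a relative margin and the radius of a 95% interval, so neither describes what is written.

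Finally, the clustered figures depend on correlations that the documents do not supply, and Section 9.1 defers analysis detail to a separate statistical analysis plan, which may deal with repeated readings. That is correct. The arithmetic error does not rely on those figures, and a separate plan cannot make this sentence true.

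**Conclusion.** The stated precision is wrong as written. At 70% accuracy with 135 independent readings, the two-sided 95% half-width is 7.7 points (11.0% relative) against the stated 7.0 points (10%). The conclusion holds under every standard two-sided interval tried. Independence is a favourable assumption here: any positive within-person correlation widens the interval, to about 9 to 12.5 points if the ICC lies between 0.2 and 0.8, which is an assumed range. If readings are independent, analytes with accuracy of about 74% or more would meet the 10% margin; with correlation, that threshold rises (about 80%, 85% and 88% at assumed ICCs of 0.2, 0.5 and 0.8). The point should be fixed, but it does not invalidate the study or alter its success criterion.

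**What to change.** Keep the sample size. In Section 8 and in the Protocol Summary, replace the precision sentence with:

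> With 45 participants and 3 visits (135 readings) and 70% accuracy, the 95% CI half-width is 7.7 percentage points (11.0% of the estimate) if readings are independent; assuming, for illustration, a within-participant correlation of 0.2 to 0.8, it is about 9 to 12.5 points (13% to 18%).

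This also defines the margin as half-width divided by the estimate. If the sponsor prefers not to print a correlation range that has no source in the documents, the minimum is the 7.7-point (11.0%) figure, the words stating that it assumes independence, and a note that positive correlation between a participant's visits would widen it. Section 2.2.1 needs no edit.

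The cost is one sentence in two places and a less favourable stated precision. Enrolment and procedures do not change.

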**Study endpoints** 

The **primary endpoint** of the study is to determine the Vitastiq device accuracy and performance. The goal is to achieve at least 70% Vitastiq accuracy performance meaning that at least 70% of Vitastiq readings for each mineral and vitamin fall within the range of matching blood test results.

The **secondary endpoint** of the study is to define repeatability of Vitastiq readings method. The goal is to achieve at least 80% Vitastiq readings method repeatability meaning that at least 80% of Vitastiq readings for each mineral and vitamin performed by less experienced investigator and participant fall within the range of matching Vitastiq readings performed by the most experienced investigator.

Statistical analysis

Statistical analysis of primary study outcome will be based on calculation of 95% confidence interval (CI) of the estimated accuracy of Vitastiq readings for each mineral or vitamin. The expected accuracy level is 70%, therefore by using 135 readings the radius of 95% confidence interval would be estimated with 10% relative margin of error. The point estimate of the accuracy value together with 95% CI will be presented for each mineral or vitamin

Statistical analysis of secondary outcomes will include Kappa statistic for interrater reliability on Vitastiq readings or Friedman ANOVA for testing the possible change of each mineral/vitamin blood level during the study period. Kappa statistic for interrater reliability will be calculated separately for each analyte and for all 135 readings. Additionally, the results of the second and the third rater (second investigator and participant) will be separately compared to the results of the first rater (first investigator). In Friedman ANOVA test 3 consecutive blood test results, that is on day 1, 29, and 57, will be compared.

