#### 1.3 STUDY PURPOSE

The purpose of the study is to test the accuracy of Vitastiq device as a personal tracker of vitamins and minerals in human body and to obtain and analyse data to enhance the accuracy of new version of Vitastiq device.

The main objective is to define the accuracy of Vitastiq device. Data (readings) obtained by Vitastiq will be compared to blood test results obtained by commonly used analytical methods. Both, Vitastiq readings and blood sampling will be taken at the same time. Vitastiq accuracy performance for each mineral and vitamin reading is considered acceptable if at least 70% of Vitastiq readings fall within the range of matching blood test results.

The study should provide answers to two main questions:

- a) Do 70% of Vitastiq readings for each mineral and vitamin fall within the range of matching blood test results?
- b) Is Vitastiq reading method at least 80% repeatable where the readings performed by the most experienced investigator are compared to the readings performed by less experienced investigator and participant.

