#### 2.2.2 Secondary endpoints

Three Vitastiq readings by two investigators (who differs in years of experiences in performing EAV readings by Vitastiq device) and by the participant in the study will be performed and one blood sample will be collected per participant at each visit (on day 1,  $29 \pm 4$  days and  $57 \pm 4$  days). The purpose of the secondary endpoint is to determine repeatability of Vitastiq reading method. Therefore, the results of Vitastiq readings performed by less experienced investigator and by participant will be compared to the results of Vitastiq readings collected by the most experienced investigator. The goal is to achieve at least 80% Vitastiq reading method repeatability meaning that at least 80% of Vitastiq readings for each mineral and vitamin performed by less experienced investigator and participant fall within the range of matching Vitastiq readings performed by the most experienced investigator.

Using Vitastiq device the participants will measure their level of minerals and vitamins on daily basis. The results of each mineral and vitamin will be presented as low, normal or high (see Table 1 above). Participants will receive their numerical blood sample results of previous visit at next visit. The aim of

third study endpoint is to define which results/information (obtained by Vitastiq device or well-established blood test analyses) has bigger impact on people's life style changes (food intake, additional exercises).

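### The 80% repeatability goal is a percentage of matching readings, but the only statistic named for the readings is kappa; the percentage has no confidence interval, and the goal is not tied to each operator

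*Combined protocol and SAP*

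**What the plan says.** Section 1.3 introduces the aims with "The study should provide answers to two main questions", and the second of these asks "Is Vitastiq reading method at least 80% repeatable". The Protocol Summary repeats the target: "The goal is to achieve at least 80% Vitastiq readings method repeatability". Section 2.2.2 gives the unit: "at least 80% of Vitastiq readings for each mineral and vitamin performed by less experienced investigator and participant" are to match the readings of the most experienced investigator. The goal is therefore a percentage of matching readings, set for each analyte.

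On analysis, section 8 says "Statistical analysis of secondary outcomes will include Kappa statistic for interrater reliability on Vitastiq readings", with Friedman ANOVA as the other named method; that test is for blood levels, not for the readings. It continues: "Kappa statistic for interrater reliability will be calculated separately for each analyte (vitamin and mineral) and for all 135 readings". The Protocol Summary says the same: "Kappa statistic for interrater reliability will be calculated separately for each analyte and for all 135 readings". Section 8 adds that the second investigator and the participant will each be compared separately with the first investigator. It names no statistic for that comparison and does not mention 80% there.

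The primary endpoint is treated differently. For that percentage section 8 states: "The point estimate of the accuracy value together with 95% CI will be presented for each mineral or vitamin". No such sentence exists for the repeatability percentage. Sections 7.2 and 9.1 leave the detail to a separate statistical analysis plan, which is not among the supplied documents.

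**The concern.** An analysis that follows section 8 as written yields a kappa per analyte. Nobody can hold a kappa against an 80% goal, because the same percentage agreement corresponds to very different kappas depending on how the readings spread over LOW, NORMAL and HIGH. One of the study's two main questions would be left without a matching estimate or a statement of its uncertainty.

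The wording of the goal also names two operators together. If their readings are pooled, a good result from the second investigator can carry a poor one from the participant. That matters here because section 1.2 describes the device as one for personal use, so the participant's own agreement is of direct interest. Finally, the supplied text does not say whether the observed percentage or a confidence limit has to reach 80%.

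**Working it through.** **Inputs from the documents.** 45 participants and 3 visits (section 2.2.1) give 45 × 3 = 135 readings per operator and analyte. With three operators this is 405, which agrees with section 2.2.1. The goal is 80%, and there are three categories. The plan gives no precision figure for the repeatability goal; its 10% relative margin belongs to the primary endpoint and is not used here.

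**Assumptions (not in the documents).** The distributions of readings over LOW/NORMAL/HIGH, taken as equal for both raters; the example counts; and the within-participant correlation ρ, varied from 0 to 1.

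**1. Kappa at exactly 80% agreement.** κ = (0.80 − pe)/(1 − pe), where pe is the sum of the squared category shares.

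| LOW/NORMAL/HIGH | pe | κ |
|---|---|---|
| even thirds | 0.333 | 0.467/0.667 = 0.70 |
| 15/70/15 | 0.0225 + 0.49 + 0.0225 = 0.535 | 0.265/0.465 = 0.57 |
| 10/80/10 | 0.01 + 0.64 + 0.01 = 0.66 | 0.14/0.34 = 0.41 |

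One percentage gives three kappas, so kappa cannot show whether 80% was reached.

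**2. Each operator or pooled.** Let the second investigator match on 122 of 135 (90.4%) and the participant on 94 of 135 (69.6%). Pooled: (122 + 94)/270 = 216/270 = 80.0%, goal met. Judged per operator, the participant falls short by 10.4 points.

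**3. Point estimate or confidence limit.** If the point estimate decides, 0.80 × 135 = 108 matches suffice. The Clopper-Pearson 95% interval for 108/135 is 72.3% to 86.4%. If the lower limit must reach 80%, 117/135 is not enough (lower limit 79.7%) and 118/135 = 87.4% is the first count that is (lower limit 80.6%). These limits treat the 135 readings as independent; positive correlation between a participant's visits would widen the interval and tend to raise the count.

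**4. Width of the missing interval.** Half-width = 1.96 × √(0.80 × 0.20/n_eff), with n_eff = 135/(1 + 2ρ) for three visits per participant.

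| ρ | n_eff | half-width |
|---|---|---|
| 0 | 135 | 6.7 points |
| 0.5 | 67.5 | 9.5 points |
| 1 | 45 | 11.7 points |

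**5. Why kappa is still useful beside the percentage.** With 5/90/5, pe = 0.0025 + 0.81 + 0.0025 = 0.815, so two unrelated raters agree on 81.5% on average. They reach 108 of 135 with probability P(Bin(135, 0.815) ≥ 108) = 0.72. With 10/80/10 that probability is 0.0003. Chance agreement is an issue only where NORMAL dominates strongly.

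**The case against.** The strongest reply is that much of this is already covered or properly deferred. The percentage follows directly from the definition in section 2.2.2 and can be counted. Section 8 says only that the secondary analysis will include kappa, which does not exclude reporting the percentage. The two operators are to be compared separately with the first investigator, so both results should be visible. Interval method and decision rule are ordinary content of a separate analysis plan, and this is formally a secondary endpoint.

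Most of this stands, and it limits the point. A reader might infer that no operator-wise analysis is planned; section 8 says otherwise, and only the link to 80% is missing. A reader might infer that the rule will be chosen after the data are seen; the separate plan may well fix it, and we cannot tell. A reader might take the goal to require that both operators match at the same visit; section 2.2.2 counts readings, not visits, so that reading has little support in the text. A reader might also conclude that the 80% goal can be met by chance; this depends on a distribution that the documents do not give.

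What the reply does not remove is the mismatch. The method section names a statistic that does not answer the stated question, while for the primary percentage it does promise an estimate with an interval.

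**Conclusion.** The point holds for the supplied text. The repeatability goal is a percentage, and the one statistic named for the readings does not estimate it: at 80% agreement kappa runs from 0.41 to 0.70 over the three illustrative distributions. The planned operator-wise comparisons are not tied to the goal, and the percentage has no interval. The omitted uncertainty is 6.7 to 11.7 points either side at 80%, depending on how strongly a participant's visits are correlated. The open decision rule spans 108 to 118 matches of 135 under independence.

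The 122 and 94 example was chosen to fall exactly on 80.0% when pooled; it shows that a reversal is possible, not that it is likely. The data remain usable whatever is decided, so this is a change that should be made rather than a flaw that invalidates the study. If the separate analysis plan already contains these statements, section 8 and the Protocol Summary need only be aligned with it.

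**What to change.** In section 8 and the Protocol Summary, and with section 2.2.2 made to match, state the following.

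- For each analyte, the percentage of readings in the same category (LOW, NORMAL, HIGH) as the first investigator is reported separately for the second investigator and for the participant. Each has a 95% CI that accounts for three visits per participant, for example from a bootstrap that resamples participants.
- The 80% goal is judged on this percentage for each operator, in line with the separate comparisons already planned.
- The plan says in advance whether the point estimate or the lower confidence limit decides.
- Pairwise kappa with its CI, and each rater's distribution over the three categories, are shown beside the percentage as descriptive context for chance agreement.

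Kappa should not become a second pass/fail condition. In a simulation at assumed 5/90/5 distributions with a true kappa of 0.2 (45 × 3 independent readings, participant bootstrap), about 96% of runs reached 80% agreement but only about 38% also had a lower kappa limit above 0. Such a condition would often withhold the claim although agreement is truly better than chance.

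The cost is a few sentences and one table from data already collected. There are two downsides: the goal is harder to meet than under pooling, and the interval that respects repeated visits is wider, with a half-width at 80% of up to 11.7 instead of 6.7 points.
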